5.2.1 Primary pre-specified analysis

Outcome Variable: the occurrence of FRI, as a binary outcome. We will denote this by Y_i , for person i . For each individual, we also record the time under observation, T_i . This value will be censored at the end of the follow-up time. [17]

Primary Analysis: the primary analysis will be conducted as a binomial regression with the complementary log-log link. This allows the available person-time to be used.

The estimated effect will be the relative hazard.

The analysis will be two-sided, with a type I error rate (alpha) of 0.05. Because there is no intention of including patients from this pilot trial into a subsequent definitive study, each trial (pilot and definitive) is completely separate, with an independent alpha.

5.2.2 Additional analyses

Supplemental analyses. These analyses are designed to provide additional insight and support for the primary analysis, and to assess whether or not the methodological choices we made had an undue effect on the results. In reporting, they will be sharply distinguished from the primary outcome, and will not be highlighted as central or determinative findings in reports, publications,

abstracts, posters or other communications.

Additional sensitivity analyses will be conducted based on the following variables as base- line covariates: Gustilo fracture type, lower extremity fracture, wound contamination, time from injury to first debridement, antiseptic wound dressing in the emergency department, method of fixation, wound closure at initial debridement, age, work-related injury, and employment status. Such analyses will be reported descriptively and with confidence intervals, but no significance P- values will be given. Conclusions based on such subgroups or adjustments will be considered hypothesis-generating, and will not form the basis for highlighting in reports or publications.

Fisher’s Exact Test. We will report the results of Fisher’s exact test on the 2×2 cross- tabulation of the reoperation binary outcome and the treatment assignment. This does not take into account observation time. This is an independent statistical procedure, and may yield statistically inconsistent results.[◦]

Risk difference. We will report the 95% confidence interval for the risk difference between the groups. Because this will be conducted by an independent regression (binomial regression with the identity link), these new findings may be statistically inconsistent with the main analysis. Thus, we will only report 95% confidence intervals, omitting P-values. The risk difference is interpretively important and may be useful in future meta-analytic studies.

Combined analysis. At the conclusion of both trials, an additional analysis will be conducted in which both data sets are combined into a single analysis. This analysis, bearing similarity to a meta-analysis of original data, will yield a combined effect estimate and confidence interval. deviation. No P-value will be reported. Thus, this secondary analysis does not constitute an additional risk for declaring significance and no multiple comparison adjustment is mandated.

Statistical considerations. Intent to treat analysis is recommended, but impossible when the primary outcome is missing. We will conduct exploratory regression of missingness, and observation time, using the following predictors: gender, severity of injury, distance to clinic, and age.

Secondary analyses. All secondary analyses will be sharply distinguished from the primary pre-specified analysis and will be identified as such. Secondary analyses include outcome variables or planned subsets, which contribute either additional insight or address different scientific questions than the primary analysis.

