Diagnosis and Main Inclusion Criteria	All patients 18 years of age or older who present to Muhimbili Orthopaedic Institute (MOI) for treatment of Gustilo-Anderson (GA) Type I, II or IIIA open tibia fractures will be screened for participation. Eligible patients must present to the hospital within 48 hours of their injury and receive surgical debridement of their open fracture wound within 7 days of their injury. The open wound must be primarily closable at the index debridement.
Treatment Groups	The pGO-Tibia trial will compare two solutions: 1) aqueous gentamicin solution (2mg/mL) in normal saline, or 2) normal saline only. A minimum of 5mL and a maximum of 40 mL of either solution will be injected into the fracture site immediately following primary closure of the traumatic wound.

Randomization	Allocation to the study groups will be performed using a web-based randomization. The randomization sequence was generated using randomly permuted blocks of 4, 6, and 8 with a 1:1 allocation ratio.
Study Outcomes	The definitive trial primary outcome is occurrence of FRI. Secondary outcomes of the definitive trial are the occurrence of 1) nonunion, and 2) unplanned fracture-related reoperation within 12 months of definitive fixation. Definitive trial subsidiary outcomes include health-related quality of life, radiographic healing, and clinical healing. A blinded adjudication process will judge each study event on occurrence of FRIs, nonunions, and unplanned fracture-related reoperations.
Feasibility Outcomes	This pilot trial will focus on the following feasibility endpoints: Recruitment: number of patients screened, number and proportion of patients screened that are eligible, enrolled, randomized, and receive intervention. Retention: number and proportion of randomized patients who attend each follow-up visit. Data collection completeness, solution quality control, masking and concealment, and evaluation of primary and secondary outcomes (reliability of fracture-related infection and mRUST scoring, radiographic image quality, and completeness of EQ-5D and FIX-IT).
Follow-Up	Study participants will be followed at 2 weeks, 6 weeks, 3 months, 6 months, 9 months, and 12 months from their fracture.
Sample Size	50 individuals per arm will be included in the feasibility trial.

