5.0 STATISTICAL PLAN

5.1 Preliminary Sample size determination:

This study seeks to explore if local antibiotics are effective in reducing infection. Existing literature estimates the rate of infection after intramedullary nailing for open-tibia fracture at 6-21%, with higher rates seen in developing countries^{23,24}. Based on the previous randomized controlled trial conducted at MOI, the rate of deep infection in patients with open tibia fractures who do not receive local antibiotics during operative management was estimated to be 12%. For a relative risk reduction of 50% in the rate of deep surgical site infections, with an alpha (two-sided) of 0.05 and power of 0.80, the estimated sample size was 712 patients (356 per group). Assuming a loss to follow-up of 20%, the final sample size needed was determined to be 890 patients. Given the anticipated enrollment of 15 participants per month, enrollment would take approximately 5 years for a single center study. The study described herein is a pilot trial with a 1-year enrollment period to include 100 patients, approximately 10-20% of the necessary sample size for the definitive trial.

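### The definitive trial's primary model leaves out two severity measures assessed before randomisation, at a small cost in power, and the sensitivity covariate list needs tidying

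*Combined protocol and SAP*

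**What the plan says.** Section 5.2.1 states that "the primary analysis will be conducted as a binomial regression with the complementary log-log link" and names no covariate; the outcome table in section 5.2 names none either. The model is therefore unadjusted by omission, although the text never uses that word.

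Adjustment is confined to section 5.2.2: "Additional sensitivity analyses will be conducted based on the following variables as" baseline covariates. Ten follow. They include Gustilo type and wound contamination, and also lower extremity fracture and "wound closure at initial debridement". The results carry confidence intervals but no P-values and are labelled hypothesis-generating.

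The Study Summary sets this eligibility condition: "The open wound must be primarily closable at the index debridement". Section 4.2 excludes wounds that cannot be closed, and section 4.3 places randomisation after closure is complete. Section 4.6.3 has the surgeon classify the wound (OTA and Gustilo-Anderson) after debridement. Section 4.5 uses permuted blocks with no stratification factor. The subgroup list in section 4.7.2 includes Gustilo-Anderson type (1 or 2 against 3) and contamination (minimal or moderate against severe).

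Section 5.2 says that these methods mainly serve planning and that the SAP may be modified in light of the pilot.

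**The concern.** The plan treats wound type and contamination as clinically relevant by making them subgroup factors, and has both in hand before allocation. It then uses them neither to stratify randomisation nor in the model that will decide the definitive trial. If they predict infection, some power is lost. If the choice of covariates stays open until outcome data exist, a later adjusted analysis will carry little weight.

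The list that does provide for adjustment contains one item that cannot vary among randomised patients and another that cannot vary on its most natural reading.

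**Working it through.** **Inputs from the plan (section 5.1).** The infection rate in patients who "do not receive local antibiotics during operative management was estimated to be 12"% gives a control risk of 0.12. "For a relative risk reduction of 50% in the rate of deep surgical site infections" gives a treated risk of 0.06. The stated size is: "with an alpha (two-sided) of 0.05 and power of 0.80, the estimated sample size was 712 patients (356 per group"). Then: "Assuming a loss to follow-up of 20%, the final sample size needed was determined to be 890 patients".

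**Reproducing the stated size.** With pooled variance and mean risk 0.09:

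n = [1.960·√(2·0.09·0.91) + 0.842·√(0.12·0.88 + 0.06·0.94)]² / 0.06² = 355.9, so 356 per arm and 712 in all; 712/0.80 = 890. The plan's figures reproduce exactly. On the complementary log-log scale the target is ln(0.94)/ln(0.88) = 0.484.

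**Power with and without severity covariates.** The documents give neither the prevalence nor the prognostic strength of the severity factors, so both are assumed. I simulated 4,000 trials per setting at 356 per arm, holding the marginal risks at 12% and 6%:

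| Assumed prevalence | Assumed hazard ratios | Power unadjusted | Power adjusted | SE of log relative hazard (unadjusted, adjusted) |
|---|---|---|---|---|
| 35% | 1.5 | 0.804 | 0.806 | 0.267, 0.267 |
| 35% | 2 | 0.797 | 0.804 | 0.266, 0.267 |
| 35% | 3 | 0.801 | 0.816 | 0.267, 0.267 |
| 35% | 4 | 0.797 | 0.817 | 0.268, 0.268 |
| 35%, 20% | 2, 2 | 0.803 | 0.817 | 0.267, 0.268 |
| 35%, 20% | 3, 2 | 0.792 | 0.811 | 0.267, 0.267 |
| 35%, 20% | 3, 3 | 0.799 | 0.827 | 0.267, 0.268 |
| 35%, 20% | 4, 4 | 0.806 | 0.845 | 0.267, 0.269 |

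The gain runs from 0.3 to 3.9 points. A second set, with 40% type IIIA and 25% severe contamination, agrees: 0.809 to 0.819 at hazard ratios 2.5 and 2, and 0.824 to 0.853 at 4 and 3.

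**Where the gain comes from.** The standard error never falls; the coefficient moves. In the last row of the table the median relative hazard goes from 0.473 to 0.456, so |log|/SE goes from 0.749/0.267 = 2.80 to 0.785/0.269 = 2.92.

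**Chance imbalance.** The hypergeometric probability that the arms differ by 10 points or more in a binary factor with prevalence 20% to 50% is 0.1% to 0.9% at 356 per arm. It is 21% to 40% at the pilot's 50 per arm.

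To size a typical imbalance in the definitive trial, assume 40% type IIIA with hazard ratio 2.5. The SD of the between-arm difference is √(2·0.4·0.6/356) = 3.7 points. Control-arm risks are 7.8% (I/II) and 18.3% (IIIA), a gap of 10.5 points. A one-SD imbalance then shifts the risk difference by at most 0.037 × 10.5 = 0.4 points. The standard error of the risk difference is √(0.12·0.88/356 + 0.06·0.94/356) = 2.1 points.

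**Events available.** The definitive trial expects 356 × (0.12 + 0.06) = 64 infections, or about 21 per coefficient for treatment plus two covariates. The pilot expects 50 × 0.18 = 9, or 3 per coefficient.

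**The covariate list.** A wound that cannot be closed at the index debridement is excluded, and allocation follows closure. Wound closure at initial debridement thus has one value in every randomised patient, is collinear with the intercept and cannot be estimated. Lower extremity fracture behaves in the same way if it means the index fracture, since all patients have an open tibial shaft fracture. If it means an associated fracture it can vary: Table 1 excludes bilateral open tibial fractures but not other additional leg fractures.

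**The case against.** An unadjusted comparison under 1:1 permuted-block randomisation is valid. Its standard error and type I error already allow for chance imbalance. Adjustment for both severity factors is planned as a supplement, and section 5.2 leaves the SAP open to revision after the pilot. All of this stands, so the point concerns the choice of headline model and not an error in it.

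Three stronger readings are tempting, and the documents do not support them:

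- A reader might infer that severity imbalance biases the primary result. It is ordinary sampling variation, and a large imbalance is rare at 356 per arm. The 21% to 40% figure belongs to the pilot, whose feasibility outcomes are summarised without inference; it is no argument for changing the definitive model.
- A reader might infer that the plan gives up free precision. In this model adjustment does not reduce the standard error of the log relative hazard. The gain comes with a change of target, from a marginal to a conditional effect.
- A reader might infer that both questionable covariates are certainly constant. Only wound closure is. Lower extremity fracture is undefined.

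It is also fair to say that section 5.2.2 does not state that all ten covariates enter one model, and that a constant term would simply be dropped without biasing anything.

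**Conclusion.** The point holds as a modest improvement to the definitive trial's analysis. Two severity measures that the plan itself treats as relevant are available before allocation and absent from the primary model. The cost is about 0 to 4 points of power at 356 per arm. That range rests on assumed prevalences of 20% to 40% and hazard ratios of 1.5 to 4. Towards the weaker end of that range the gain is below 1 point.

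The validity of the primary analysis and the planned 356, 712 and 890 are unaffected. The more durable reason to act is pre-specification: the two covariates can be fixed now, before any definitive-trial data exist. The wound-closure item is a plain slip that needs no assumption to show.

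**What to change.** For the definitive trial, write the primary complementary log-log model with treatment, Gustilo-Anderson type (I/II against IIIA) and contamination (minimal or moderate against severe, as in the subgroup list). Report the unadjusted model as support. State that both covariates are recorded before allocation, and that the relative hazard is conditional on them. Keep the pilot analysis unadjusted.

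In section 5.2.2, delete wound closure at initial debridement. Delete lower extremity fracture, or define it as an associated additional fracture.

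The cost is SAP wording only: no new data, patients or procedures. The drawback is the conditional estimand. In the simulated settings the conditional relative hazard was 0.46 to 0.48, against 0.484 marginally. The unadjusted model and the risk difference already planned in section 5.2.2 keep marginal results in the report.

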4.7.2 Definitive Trial Outcomes

Primary Outcome

The primary outcome is occurrence of *fracture-related infection* (FRI) a binary variable. FRI diagnosis is likely to peak between 3 and 6 months after surgery and has a non-normal time-to-event distribution, with incident cases rarely presenting later than 12 months after surgery. Any of the four following diagnostic criteria are confirmatory for infection: (1) fistula, sinus or wound breakdown; (2) purulent drainage from the wound or presence of pus during surgery; (3) phenotypically indistinguishable pathogens identified by culture from at least two separate deep tissue/implant specimens; or (4) presence of microorganisms in deep tissue taken during an operative intervention, as seen on histopathological examination.

Secondary Outcomes

The following secondary outcomes will be assessed:

1. Occurrence of nonunion, a binary variable, as defined by:
 - a. Any unplanned reoperation for promotion of bone healing; OR
 - b. mRUST ≤ 10 AND either: FIX-IT score ≤ 11 at 12 month follow-up, OR recommendation by treating surgeon for nonunion repair surgery.
2. Occurrence of unplanned fracture-related reoperation, a binary variable, for infection, wound healing, or fracture union, excluding removal of implants for prominence/irritation. This may include but is not limited to:
 - a. Irrigation and debridement of surgical incisions or open fracture wounds due to infections or wound healing problems;
 - b. Revision wound closure for dehiscence;
 - c. Soft tissue coverage procedure for infected or necrotic wound;
 - d. Fracture delayed union or nonunion surgery (such as bone grafting or implant exchange);

- e. Reoperation for hardware or prosthesis failure due to infection or bone-healing problems;
- f. Amputation for infection, wound or fracture healing problem.

Subsidiary Outcomes

The following subsidiary outcomes will be assessed:

1. Radiographic healing via the mRUST score, an ordinal scale ranging from 4 to 16.
2. Clinical healing via the FIX-IT score, an ordinal scale from 0-12 that encompasses two domains, ability to weight-bear and pain at fracture site, each scored from 0-6: ability to weight-bear and pain at fracture site.
3. Health-related quality of life via EQ-5D.
4. FRI suggestive criteria, including clinical (wound redness, fever) and radiographic signs (sequestrum), elevated serum inflammatory markers, and new onset or increased wound drainage.

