5.2 Statistical Methods

Feasibility outcomes described in 4.7.1 will be summarized using means and proportions, without the use of inferential statistics. Given the principle feasibility aim of this pilot trial, the following statistical methods are described primarily for planning purposes. Statistical methodology to be performed in the analysis of each primary, secondary, and subsidiary outcome is outlined below. The statistical analysis plan (SAP) will provide additional detail on statistical analysis and will be modified as necessary based on data collected in this pilot trial.

Outcomes Analysis Planned for Definitive Trial

Outcome	Data	Method of analysis
---------	------	--------------------

Primary		
Rate of fracture-related infection	FRI criteria	Relative Hazard as estimated by two-sided binomial regression with the complementary log-log link, with a type I error rate (alpha) of 0.05.
Secondary		
Rate of unplanned reoperation	Review of complications	Fisher's exact test on the 2×2 cross-tabulation
Rate of nonunion	Nonunion criteria	
Subsidiary		
Quality of Life	EQ-5D	
Inflammatory Markers	CRP	
Radiographic Healing	mRUST	
Clinical Healing	FIX-IT	
Direct costs	TM Analysis	
Indirect costs	WPAI	
FRI Suggestive Criteria	FRI criteria	Fisher's exact test on the 2×2 cross-tabulation

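### The supplemental Fisher test in 5.2.2 is run on reoperation instead of FRI, and the planned loss regressions leave out treatment arm (minor)

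*Combined protocol and SAP*

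**What the plan says.** Section 5.2.1 makes occurrence of FRI the primary outcome, analysed by binomial regression with the complementary log-log link; of this model it says "This allows the available person-time to be used". Section 5.2.2 introduces the supplemental analyses as giving insight into and support for that analysis, and as a way "to assess whether or not the methodological choices we made had an undue effect on the results".

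The Fisher paragraph in 5.2.2 cross-tabulates "the reoperation binary outcome and the treatment assignment. This does not take into account observation time", and adds: "This is an independent statistical procedure, and may yield statistically inconsistent results". The next paragraph plans a risk difference by identity-link binomial regression. It names no outcome, but warns that "these new findings may be statistically inconsistent with the main analysis".

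The table in 5.2 lists unplanned reoperation as a secondary outcome with the method "Fisher's exact test on the 2×2 cross-tabulation". For FRI it lists only the complementary log-log regression.

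Under Statistical considerations, missingness and observation time are to be regressed on age, gender, injury severity and distance from the clinic. Sections 2.2 and 4.7.1 define retention over all randomized patients. Section 5.1 assumes 20% loss to follow-up.

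**The concern.** A supplemental analysis that tests a modelling choice has to hold the outcome fixed and change the method. This one changes both. If the reoperation test and the FRI regression disagree, the reader cannot tell whether the link function and use of person-time drove the FRI result or whether the two outcomes simply behave differently. The caveats about observation time and inconsistent results are useful mainly for a test of FRI set against the primary model.

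On loss, the plan concedes that a full intent-to-treat analysis is not possible where FRI is missing. A reader of the results will then ask whether loss was similar in the two arms. Regressions without arm cannot answer that.

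**Working it through.** **1. Are the outcomes the same?** Section 4.7.2 defines the secondary outcome as "Occurrence of unplanned fracture-related reoperation, a binary variable, for infection, wound healing, or fracture union". The same section lets FRI be confirmed by any one of four criteria, including wound breakdown or purulent drainage, which need no operation. A patient can have FRI without reoperation, or reoperation (for union, say) without FRI. The Fisher test in 5.2.2 and the one in the 5.2 table are therefore the same test of the same secondary outcome.

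**2. The plan's sample size.** With 12% v 6%, two-sided 0.05 and power 0.80 (section 5.1), the average rate is 0.09:

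n = [1.96·√(2·0.09·0.91) + 0.842·√(0.12·0.88 + 0.06·0.94)]² / 0.06² = 356 per group, 712 in total; 712/0.8 = 890, or 445 per arm.

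This matches the plan, and nothing below changes it.

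**3. Would Fisher on FRI be a usable check?** Simulation at 445 per arm, 12% v 6%, 20% loss in each arm. Assumptions not in the documents: loss at 0.5 to 3 months; FRI hazard split 25/60/15% over 0–3, 3–6 and 6–12 months; log observation time as offset. Complementary log-log power is 81–83% and Fisher-on-FRI power 79–81%. The two give the same verdict at 0.05 in about 98% of trials.

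**4. The counting rule matters.** Suppose FRI is truly 12% in both arms and loss is 15% v 25% at 6–9 months. With the same hazard split, a patient lost at the midpoint, 7.5 months, has passed 85% + 15%·(1.5/6) = 88.75% of the cumulative hazard, −ln(0.88) = 0.1278. The chance of an observed FRI is then 1 − exp(−0.1278·0.8875) = 0.107.

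- Excluding only those lost without an event: (0.85·0.12 + 0.15·0.107)/(0.85 + 0.15·0.107) = 13.6%, against (0.75·0.12 + 0.25·0.107)/(0.75 + 0.25·0.107) = 15.0%. A difference appears where none exists. In simulation Fisher rejects about 7% of the time, against about 5% for the primary model.
- Twelve-month completers only: 12% v 12%.
- All randomized, observed events counted: 0.85·0.12 + 0.15·0.107 = 11.8%, against 0.75·0.12 + 0.25·0.107 = 11.7%.

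The last rule is weaker if unequal loss is early. At a midpoint of 1.75 months the observed-event chance is 1 − exp(−0.1278·0.25·1.75/3) = 0.018, giving 0.85·0.12 + 0.15·0.018 = 10.5% against 0.75·0.12 + 0.25·0.018 = 9.5%.

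**5. What would loss by arm show?** The half-width for the arm difference at 20% loss is 1.96·√(2·0.2·0.8/n): 15.7 points at n = 50 and 5.3 points at n = 445. Fisher power for 15% v 25% loss is about 17% and 95% respectively.

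**6. What it would not show.** Assume 12% FRI in both arms and 20% loss in every group except infected gentamicin patients, who have 50% loss. Total loss in that arm is 0.12·0.5 + 0.88·0.2 = 23.6% against 20.0%, a gap of 3.6 points that lies inside ±5.3. Yet its observed FRI rate is 0.06/(0.06 + 0.704) = 7.9% against 12.0%.

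**The case against.** The purpose stated in 5.2.2 includes additional insight, and a reoperation test can offer some. Sections 5.2 and 5.2.2 agree on the method, so the text does not contradict itself. That stands: the test is redundant for the purpose, not invalid.

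A reader might infer that 5.2.2 contains no check on the FRI result. The documents do not support that. The risk difference is contrasted with the main analysis, so it evidently concerns FRI, and its identity-link regression makes no stated use of person-time. The covariate-adjusted analyses also appear to concern FRI.

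A reader might also take low agreement between Fisher on reoperation and the primary model as a measure of harm. Simulated agreement was 26–67%, but that rests on assumed reoperation probabilities (30–80% of FRI cases, 3–6% of other patients) found nowhere in the documents. It is illustrative only and shows no more than that two outcomes differ.

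Finally, the methods are described mainly for planning the definitive trial, the SAP may be modified, supplemental results may not be highlighted, and the loss regressions are exploratory. In the pilot, feasibility outcomes are "summarized using means and proportions, without the use of inferential statistics". All of this limits the consequence but leaves the case for the edit intact, since planning text is cheap to correct.

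**Conclusion.** Both parts hold as minor points. The supplemental Fisher test repeats a secondary analysis and cannot do the work 5.2.2 gives it, so one unadjusted FRI check that ignores observation time remains, with its outcome unnamed. No planned analysis compares loss between arms.

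It would be tempting to conclude that the plan inflates type I error or biases the primary result. The check does not support this: with 12% FRI in both arms and early loss of 15% v 25%, the primary model rejected in 5.8% of simulated trials with a hazard ratio of 0.99. Nor would adding arm settle whether loss is informative. It shows unequal loss, but does not detect or correct outcome-dependent loss when totals are similar.

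The textual findings need no assumptions. The agreement of about 98% and the rejection rates rest on the assumed loss timing and hazard shape and on reading the primary model as having a log-time offset. The interval widths rest only on 20% loss and the planned arm sizes.

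**What to change.** In 5.2.2:

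- Make the supplemental Fisher test a test of FRI by treatment assignment, labelled as ignoring follow-up time. Keep Fisher on reoperation only as the secondary analysis in the 5.2 table.
- Name FRI as the outcome of the risk difference.
- State one counting rule for the Fisher test that does not depend on the event: for example, FRI status among those completing 12 months, or all randomized with observed events. Do not exclude only those lost without an event. The completer rule is fair if loss is unrelated to outcome; the all-randomized rule can mislead if early loss is unequal. Read the result alongside loss by arm.
- Add treatment arm, coded A/B to preserve masking, to both the missingness and the observation-time regressions, and report loss by arm. In the pilot give counts and proportions only, in line with 5.2. State that this shows unequal loss and does not address outcome-dependent loss.

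The cost is a few words of text and a few lines of code. The outcome and allocation data are already held, and sample size, visits and masking do not change. The downside is that Fisher on FRI will usually agree with the primary model, so its value is as a transparent check and not as new evidence.

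### Unplanned reoperation is given only Fisher's exact test, which ignores follow-up time and has no effect estimate named for it, although the FRI model could be used

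*Combined protocol and SAP*

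**What the plan says.** The outcomes table in section 5.2, headed as planned for the definitive trial, gives the method for unplanned reoperation as Fisher's "exact test on the 2×2 cross-tabulation". The nonunion row below it shows no method in the text available to us. Section 5.2.2 lists Fisher's test again, on the reoperation outcome, among the supplemental analyses, and says of it: "This does not take into account observation time".

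For FRI, section 5.2.1 records each person's time under observation. It fits a binomial regression with the complementary log-log link so that person-time can be used, and reports a relative hazard.

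Section 5.2.2 also promises a 95% CI for a risk difference. It names no outcome. It contrasts that result with the main analysis, so FRI is the natural reading.

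Section 5.1 sizes the definitive trial on FRI: "For a relative risk reduction of 50% in the rate of deep surgical site infections", "with an alpha (two-sided) of 0.05 and power of 0.80", and then: "Assuming a loss to follow-up of 20%, the final sample size needed was determined to be 890 patients".

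**The concern.** The Study Summary counts reoperation within 12 months of definitive fixation, so it can be dated. It is observed through the same visits as FRI, and reoperation for infection is part of its definition in section 4.7.2. The plan gives no reason why person-time matters for one outcome and not for the other.

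Three things follow.
- A 2×2 table treats a patient lost at six weeks and a patient seen at 12 months alike, so unequal loss between arms can look like a treatment effect.
- Fisher's test is conservative, so some power is lost.
- A P-value alone cannot be set beside the relative hazard for FRI, and it gives later evidence syntheses nothing to use.

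**Working it through.** **Inputs from section 5.1.** Control rate 12%, relative reduction 50% (so 6%), two-sided alpha 0.05, power 0.80, loss 20%. Allocation is 1:1 (section 4.5).

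**Assumptions.** The documents give no reoperation rate, so 5-30% is used for size, and 12% v 6% is borrowed from FRI for power. Fisher's test is taken as two-sided.

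**1. The plan's own figure.** With pooled variance and no continuity correction:

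n = [1.960 √(2 × 0.09 × 0.91) + 0.842 √(0.12 × 0.88 + 0.06 × 0.94)]² / 0.06² = (0.793 + 0.339)² / 0.0036 ≈ 356 per group.

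That gives 2 × 356 = 712, and 712 / 0.80 = 890, or 445 per group. The plan's numbers reproduce. With the continuity correction, which approximates the size needed for Fisher's test, n is 389 per group.

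**2. Size and power at definitive scale.** All 2×2 tables are enumerated:

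rejection rate = Σ b(x₀; n, p₀) b(x₁; n, p₁) × I[P(x₀, x₁) ≤ 0.05],

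where b is the binomial probability and P is the test's P-value. At 356 per arm:

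| Quantity | Fisher | Log-log, Wald | Log-log, likelihood ratio |
|---|---|---|---|
| Size, rate 5% | 3.3% | 4.7% | 5.2% |
| Size, rate 12% | 3.8% | 4.9% | 5.1% |
| Size, rate 20% | 4.1% | 4.9% | 5.0% |
| Size, rate 30% | 4.2% | 5.0% | 5.0% |
| Power, 12% v 6% | 0.771 | 0.800 | 0.807 |

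The power loss is 0.800 − 0.771 = 0.029 to 0.807 − 0.771 = 0.036, or about 3-4 points.

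**3. Ignoring follow-up time.** Assume exponential event times, dropout times uniform over the year, dropouts counted as event-free, and a true 12-month risk of 12% in both arms.

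The hazard is λ = −ln(0.88) = 0.128. A dropout's chance of an observed event averages 1 − 0.12/λ = 0.061. With dropout of 30% v 10%, the observed risks are:
- 0.70 × 0.12 + 0.30 × 0.061 = 0.102
- 0.90 × 0.12 + 0.10 × 0.061 = 0.114

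An apparent difference of about 1.2 percentage points arises with no treatment effect. Simulation at 445 per arm (20,000 runs per row) gives these rejection rates:

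| True risks | Dropout | Fisher | Person-time test |
|---|---|---|---|
| 12% v 12% | 20% v 20% | 3.9% | 5.0% |
| 12% v 12% | 30% v 10% | 7.0% | 4.7% |
| 12% v 12% | 40% v 10% | 11.3% | 5.0% |
| 12% v 6% | 20% v 20% | 81.8% | 85.4% |

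**4. Effect estimate.** Sections 5.2, 5.2.1 and 5.2.2 read together name the relative hazard for FRI only, and a risk difference for no stated outcome. None names an estimate or CI for reoperation.

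**The case against.** **What stands.** Section 5.2 says the methods are described mainly for planning and that the SAP will be modified using pilot data, so nothing in the pilot turns on this choice. The neglect of time is the plan's own disclosed caveat, attached to an analysis that section 5.2.2 calls supplemental. Masking makes a large dropout imbalance unlikely. Fisher's test is a defensible choice for a secondary outcome that has no stated power target. All this limits the importance of the point, but it does not explain why the person-time model stops at FRI.

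**Stronger readings that a reader might infer, and that the documents do not support.**
- *Fisher runs far below 5%.* That is true at 50 per arm (2.1% at a 12% rate), but the table is for the definitive trial, where the shortfall is mild.
- *Fisher only costs power.* Under unequal dropout its error rate can exceed 5%.
- *The primary method cures the size problem at any scale.* At 50 per arm and a 12% rate the Wald test has size 2.7% and the likelihood-ratio test 5.8%. At a 5% rate they have 0.2% and 8.8%.
- *Both secondary outcomes get Fisher alone.* Section 5.2.2 names only reoperation. The empty nonunion cell may be a merged cell lost in extraction.
- *The plan offers no effect estimate at all.* The risk difference may be meant more widely, but the text does not say so.
- *A different exact test is needed.* Boschloo's test raises power at 356 per arm only from 0.771 to 0.789. That is a matter of preference.

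**Conclusion.** The point holds for unplanned reoperation as a modest improvement to the definitive SAP. The plan uses a test that it says ignores observation time, names no effect estimate for this outcome, and already contains a model that supplies both.

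The power cost is about 3-4 points at 356 per arm, if reoperation had the FRI rates. The validity cost is nil with equal dropout. It reaches a false-positive rate of about 7% under the illustrative 30% v 10% pattern. That figure depends on dropouts being counted as event-free, and the plan does not say how lost patients enter the 2×2 table. The event rates and dropout patterns are assumptions, not figures from the documents.

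**What to change.** - In the section 5.2 table, give unplanned reoperation the complementary log-log person-time model of section 5.2.1, with relative hazard and 95% CI, and define its observation time.
- Keep Fisher's test as the supplement that section 5.2.2 already describes.
- In the risk-difference paragraph of section 5.2.2, state that the estimate and 95% CI also apply to reoperation and to nonunion. Nonunion is partly a 12-month status, so a person-time model suits it less well.

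The cost is SAP wording and standard software. The only data item needed is the date of reoperation. One small drawback: at 50 per arm the log-log Wald test is also conservative, and the likelihood-ratio test is liberal at low event rates. Any pilot result should therefore be read from the estimate and its interval, not from a P-value.
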